### 8. STUDY ASSESSMENTS AND PROCEDURES

The investigator (or an appropriate delegate at the investigator site) must obtain a signed and dated ICD before performing any study specific procedures.

Study procedures and their timing are summarized in the SoA. Protocol waivers or exemptions are not allowed.

Safety issues should be discussed with the sponsor immediately upon occurrence or awareness to determine whether the participant should continue or discontinue study intervention.

Adherence to the study design requirements, including those specified in the SoA, is essential and required for study conduct.

All screening evaluations must be completed and reviewed to confirm that potential participants meet all eligibility criteria. The investigator will maintain a screening log to record details of all participants screened and to confirm eligibility or record reasons for screening failure, as applicable.

Procedures conducted as part of the participant's routine clinical management (eg, blood count) and obtained before signing of the ICD may be utilized for screening or baseline purposes provided the procedures met the protocol-specified criteria and were performed within the time frame defined in the SoA.

PFIZER CONFIDENTIAL

Page 47

In the event a participant is hospitalized, study assessments should be performed as feasible. Procedures not performed due to hospitalizations would not be considered protocol deviations.

Every effort should be made to ensure that protocol-required tests and procedures are completed as described. However, it is anticipated that from time to time there may be circumstances outside the control of the investigator that may make it unfeasible to perform the test. In these cases, the investigator must take all steps necessary to ensure the safety and well-being of the participant. When a protocol-required test cannot be performed, the investigator will document the reason for the missed test and any corrective and preventive actions that he or she has taken to ensure that required processes are adhered to as soon as possible. The study team must be informed of these incidents in a timely manner.

For samples being collected and shipped, detailed collection, processing, storage, and shipment instructions and contact information will be provided to the investigator site prior to initiation of the study.

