5.3. Methods to Manage Missing Data

For missing efficacy data other than time to event endpoints, a mixed baseline observation carried forward (BOCF)/ last observation carried forward (LOCF) approach will be used. See below:

• For efficacy endpoints related to COVID-19 targeted sign/symptoms, missing data at baseline will be treated as mild. If participant discontinues study due to AE or discontinues study at same time of treatment discontinuation due to lack of efficacy, missing data will use BOCF. Otherwise, missing data will use LOCF.

For safety data, missing and partial dates will be programmatically handled according to Pfizer standards.

PFIZER CONFIDENTIAL
Page 20

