Participants who are hospitalized for the treatment of COVID-19 or death from any cause during the 28-day period will be classified as not achieving sustained symptom alleviation/resolution and will be censored at day 25.

Cox proportional hazard model analyses will be used for time to sustained symptom alleviation/resolution. Cox proportional hazard model will include treatment and region effect as independent variables. In addition, the stratification variables specified in Section 3.5 will be added to the model analyses depending of the analysis population.

Time to sustained symptom alleviation/resolution will be summarized graphically using Kaplan-Meier plots for each of the treatment groups, the analyses will be done using the mITT population only.

In the mITT populations, the analysis will be repeated in subgroups based on baseline serology status (positive, negative), by baseline viral load ($<10^4$ copies/mL, $\ge 10^4$ copies/mL), and ($<10^7$ copies/mL, $\ge 10^7$ copies/mL).

6.2.5. Proportion of Participants with Severe Signs/Symptoms Attributed to COVID-19 through Day 28

Participants will record a daily severity rating of their symptom severity over the past 24 hours based on a 4-point scale in which 0 is reported if no symptoms were present; 1 if mild; 2 if moderate; and 3 if severe.

Vomiting and diarrhea will each be rated on a 4-point frequency scale where 0 is reported for no occurrence, 1 for 1 to 2 times, 2 for 3 to 4 times, and 3 for 5 or greater. Sense of smell and sense of taste will each be rated on a 3-point Likert scale where 0 is reported if the sense of smell/taste was the same as usual, 1 if the sense of smell/taste was less than usual, and 2 for no sense of smell/taste.

The proportion of participants with any severe targeted signs/symptoms attributed to COVID-19 through Day 28 will be summarized by treatment group. A participant with severe score for any targeted symptoms post-baseline will be counted as severe. Proportions for each targeted signs and symptom with severe category only will be plotted over time through Day 28. Additionally, the proportion of participants reporting the presence of each targeted sign and symptom that is mild, moderate or severe categories will also be presented. In addition, to understand the severity of signs/symptoms attributed to COVId-19, the following analysis will be performed:

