For duration of each targeted COVID19 sign/symptom, a Kaplan-Meier analysis providing the median and quartiles will be provided for each treatment group for mITT population set. Two additional figures (Number of Participants and Median Time to Sustained Alleviation of Each Targeted Sign/Symptom by Treatment Group [mITT) will be included for the endpoint of Duration of Each Targeted COVID-19 Sign/Symptom.

6.2.7. Progression to a Worsening Status in 1 or More Self-reported COVID-19 Associated Symptoms through Day 28

Participants will record a daily severity rating of their symptom severity over the past 24 hours based on a 4-point scale in which 0 is reported if no symptoms were present; 1 if mild; 2 if moderate; and 3 if severe. Vomiting and diarrhea will each be rated on a 4-point frequency scale where 0 is reported for no occurrence, 1(mild) for 1 to 2 times, 2 (moderate) for 3 to 4 times, and 3 (severe) for 5 or greater.

Progression to a worsening status for any targeted symptom will be derived programmatically based upon increasing severity (ie, the first time any targeted symptoms worsen after treatment relative to baseline):

Progression to worsening (Yes/No)	
Increasing severity	Yes
Not increasing severity	No

The proportion of participants with progression (increasing severity for any targeted symptom) will be summarized by treatment group. Treatment comparison between groups will be presented as odds ratios with 95% confidence intervals and P-value based on logistic regression model as specified in Section 6.1.1.2. The analyses will be done using mITT, mITT1, and mITT2 population. Missing severity at baseline will be treated as mild.

6.2.8. Proportion of Participants with a Resting Peripheral Oxygen Saturation ≥95% at Days 1 and 5

The oxygen saturation level will be measured for each participant. A resting peripheral oxygen saturation will be derived programmatically based on the following table:

Oxygen saturation (Yes/No)	
≥95%	Yes
<95%	No

PFIZER CONFIDENTIAI	
Page 26	

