Proportion of participants with COVID-19 related hospitalization or death from any cause through Day 28.	Subgroup Analysis for primary endpoint	mITT	Subset analysis identified in Section 6.4.	Kaplan-Meier method
Time to sustained alleviation and time to sustained resolution of all targeted signs/symptoms	Secondary analysis	mITT & mITT1 & mITT2	All data collected will be included regardless of intercurrent events. Missing severity at baseline will be treated as mild.	Cox proportional hazard model
through Day 28.			Use stratification variables as in Section 3.5.	
Time to sustained alleviation of all targeted signs/symptoms through Day 28.	Subgroup Analysis of secondary endpoint	mITT	All data collected will be included regardless of intercurrent events. Missing severity at baseline will be treated as mild. Use stratification variables as in Section 3.5.	Cox proportional hazard model
			Subset analysis by baseline serology status and baseline viral load.	
Time to sustained resolution of all targeted signs/symptoms through Day 28.	Subgroup Analysis of secondary endpoint	mITT	All data collected will be included regardless of intercurrent events. Missing severity at baseline will be treated as mild. Use stratification variables as in Section 3.5.	Cox proportional hazard model
			Subset analysis by baseline serology status and baseline viral load.	
Proportion of participants with severe signs/symptoms attributed to COVID-19 through Day 28.	Secondary analysis	mITT, mITT1 & mTT2	All data collected will be included regardless of intercurrent events. Use BOCF/LOCF for missing data. Use stratification variables as in Section 3.5.	Kaplan Meier method Logistic regression

Endpoint	Analysis Type	Population	Data Inclusion and Rules for Handling Intercurrent Events and Missing Data	Analysis Model
Proportion of participants with severe signs/symptoms attributed to COVID-19 through Day 28.	Subgroup Analysis of secondary endpoint	mITT	All data collected will be included regardless of intercurrent events. Use BOCF/LOCF for missing data. Use stratification variables as in Section 3.5.	Logistic regression
Day 20.			Subset analysis by baseline serology status and baseline viral load.	
Duration of each targeted COVID-19 sign/symptom.	Secondary analysis	mITT, mITT1 & mTT2	All data collected will be included regardless of intercurrent events. Missing data will not be imputed.	Descriptive statistics

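### The severe-symptom and worsening endpoints rest on diary scores alone, so a COVID-19 hospitalization or death with no earlier qualifying entry is scored as a non-event

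*SAP*

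**What the plan says.** **Severe symptoms (SAP 6.2.5).** The counting rule is "A participant with severe score for any targeted symptoms post-baseline will be counted as severe". The same measure is also reported for baseline, Days 2 to 6 and Days 7 to 28. Arms are compared by logistic regression.

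**Worsening (SAP 6.2.7).** The event is "the first time any targeted symptoms worsen after treatment relative to baseline", again from diary ratings and again by logistic regression, with a p-value.

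**Alleviation and resolution (SAP 6.2.4).** Participants hospitalized for COVID-19 or dying within the 28 days "will be classified as not achieving sustained symptom alleviation/resolution and will be censored at day 25".

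**Missing data (SAP 5.3).** For targeted symptoms, baseline is carried forward after study discontinuation for an adverse event, or for lack of efficacy when treatment stops at the same time. "Otherwise, missing data will use LOCF". Death is not named there, although Protocol 7.2 lists it as a reason for leaving the study.

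**Appendix 1 of the SAP.** For both endpoints: "All data collected will be included regardless of intercurrent events. Use BOCF/LOCF for missing data". It lists Kaplan-Meier and logistic regression for the severe endpoint, and logistic regression alone for worsening. SAP 5.2.1 sends both endpoints to a method like that of the primary endpoint, which is Kaplan-Meier.

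**Diary entries in hospital (Protocol 8 and 8.1.1).** "In the event a participant is hospitalized, study assessments should be performed as feasible". Procedures missed because of hospitalization are not deviations, and the diary accepts entries only within a fixed window, such as 24 hours.

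**The concern.** Alleviation, severity and worsening all serve one secondary objective, the duration and severity of symptoms. For alleviation, hospitalization or death is an unfavourable result. For the other two it has no effect. A participant admitted on Day 6 whose diary never reached the threshold is a failure on one measure and a favourable result on the other two.

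The participants affected are those with the worst course, and if the treatment works there are more of them on placebo. Leaving them out of the event count removes more placebo events than active events and understates any benefit on these two endpoints. Diary gaps around these events are foreseeable: entries may not be feasible in hospital, missed days cannot be filled in later, and there are none after death.

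**Working it through.** **1. The plan's own figure.** SAP 2.3 gives 7% on placebo, a 3.5-point difference (so 3.5% on active), two-sided 5%, 90% power, and 1717 participants. With 1:1 allocation and a pooled two-proportion test, the mean rate is 0.0525 and

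n per arm = [1.960 × √(2 × 0.0525 × 0.9475) + 1.282 × √(0.07 × 0.93 + 0.035 × 0.965)]² / 0.035² = 852 (rounded up), or 1704 in total.

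This is within 1% of 1717, and the small excess fits an allowance for the interim look. At 1717 / 2 = 858.5 per arm, the expected numbers hospitalized or dead are 858.5 × 0.07 ≈ 60 on placebo and 858.5 × 0.035 ≈ 30 on active.

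**2. The rules applied to example participants who die on Day 6**

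| Baseline, then diary | Severe? | Worse? |
|---|---|---|
| Mild, stays mild | No | No |
| Moderate, stays moderate | No | No |
| Mild, rises to moderate | No | Yes |
| Severe, falls to moderate, last value carried forward | No | No |
| Severe, falls to moderate, baseline carried forward | Yes, if imputed values count | No |

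Both are ever/never endpoints through Day 28. Carrying the last value forward only repeats a recorded score, so it neither creates nor removes a first event. Carrying baseline forward can never produce worsening. It can produce a severe score only from a severe baseline.

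**3. Size.** Let h be the rate of hospitalization or death in an arm, s the severe rate among everyone else (equal in both arms), and f the share of hospitalized or dead participants with no qualifying entry (equal in both arms). The documents give neither s nor f, so both are assumptions.

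- Rate as written: (1 − h)s + h(1 − f)
- Rate if the event counts: (1 − h)s + h
- Loss within an arm: hf
- Loss in the difference between arms: (0.07 − 0.035)f = 3.5 points × f, whatever s is

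The last two columns illustrate this with s = 20%. Counting the events gives 25.6% − 22.8% = 2.80 points.

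| f | Uncounted, placebo / active | Loss (points) | Difference as written | Difference if counted |
|---|---|---|---|---|
| 10% | 6 / 3 | 0.35 | 2.45 | 2.80 |
| 25% | 15 / 7.5 | 0.875 | 1.93 | 2.80 |
| 50% | 30 / 15 | 1.75 | 1.05 | 2.80 |
| 100% | 60 / 30 | 3.50 | −0.70 | 2.80 |

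**The case against.** The strongest reply is that these endpoints ask what symptoms participants recorded. Alleviation requires four consecutive recorded days, so it needs a rule for those who cannot supply them; an ever/never measure of recorded symptoms does not. The SAP gives no separate estimand for supportive measures and says that data are used whatever intercurrent events occur. Counting hospitalization or death makes a composite that partly repeats the primary endpoint. The events are also not lost from the report: they are the primary endpoint, and Week 24 mortality and hospital and ICU days are reported too. This stands as an argument about which version should be the main one. It does not argue against showing the other version alongside.

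The share affected is also unknown. Exclusion criterion 2 removes people expected to need admission within 48 hours, and the diary can be completed on a personal device, so many participants should have entries before admission and some may continue in hospital. That stands, and it is why the size is given as a range.

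A reader might infer four stronger things that the documents do not support:

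- **That no severe entry also means not worse.** A rise from absent to mild, or mild to moderate, on any of the 11 targeted symptoms already counts as worsening.
- **That carrying the last value forward causes the loss.** The cause is the event definition. In the Day 7 to 28 analysis, carry-forward can even keep a last severe score in the count.
- **That scoring as a non-event is settled under every method.** Under Kaplan-Meier, which SAP 5.2.1 and Appendix 1 also point to, a death could be censored instead. It would still not count, and the censoring would be informative.
- **That 3.5 points is the expected loss.** It requires that no hospitalized or dead participant recorded a qualifying score.

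**Conclusion.** The gap is real and its consequence is limited. Under logistic regression, hospitalization or death without an earlier qualifying entry is scored favourably on both endpoints, apart from the severe-baseline exception, in contrast to SAP 6.2.4.

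The loss is 3.5 points × f, resting on the design rates and on f being equal in the two arms. If the shares differ, the loss is 7f(placebo) − 3.5f(active), which stays positive unless the active share is more than twice the placebo share. Within that limit the bias is toward no difference, and at the extreme the apparent direction can reverse. It works against showing a benefit, so it is not a route to a false efficacy claim.

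Both endpoints are supportive and outside the three endpoints that SAP 5.1 lists for the Hochberg procedure. Protocol 9.1 does not restrict that procedure to three, and 6.2.7 reports a p-value, so the results may still be read as evidence. The primary analysis and the 1717 are unaffected. This is a low-cost improvement to make.

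**What to change.** 1. In SAP 6.2.5 and 6.2.7, report two versions side by side: the diary-only endpoint, and one in which COVID-19-related hospitalization or death from any cause through Day 28 counts as an event, consistent with 6.2.4.
2. For the period analyses in 6.2.5, assign the event to the period in which it occurs (Days 2 to 6 or Days 7 to 28).
3. State in SAP 5.3 how symptom data after death are handled.
4. Reconcile SAP 5.2.1 and Appendix 1 (Kaplan-Meier) with 6.2.5 and 6.2.7 (logistic regression), so that one method is named for each endpoint.

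The cost is SAP wording and programming for one extra analysis per endpoint in each population. It needs no new data and no change to the sample size. The added version is a composite that partly repeats the primary endpoint and should be labelled as such; keeping the diary-only version beside it shows how much of any difference comes from symptoms.

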### 9.3.1. General Considerations

Descriptive statistics for all efficacy endpoints by treatment group and visit will be provided.

The number of participants screened, randomized to the double blind treatment phase, completing the study drug administration, and completing the study will be summarized from the FAS. The reason for all discontinuations will be summarized by treatment group.

Baseline demographic and other characteristics will be tabulated for the FAS and summarized by treatment group. Quantitative variables will be described by standard descriptive statistics (mean, standard deviation, minimum, and maximum), and qualitative variables will be summarized by frequency tables with number and proportion in each category (with the corresponding sample sizes).

For continuous endpoints, an MMRM analysis of covariance model will be used to analyze change from baseline over time. Estimated mean differences between treatments and their respective 95% CI and p-values will be calculated.

For binary endpoints, proportion of participant with the event will be summarized for each group. Treatment comparison between the group will be presented as the difference of proportions with its 95% confidence interval using a similar analysis method as the primary endpoints.

For categorical endpoints, proportion of participant for each category will be summarized for each group.

For count endpoints, the total number of the events and average number of events will be summarized for each group.

For time-to-event endpoints (ie, time [days] to sustained alleviation/resolution of all targeted signs/symptoms through Day 28 and duration of each targeted COVID-19 sign/symptom),

2 analyses will be provided: (1) a Cox proportional hazard regression model where the estimate of the hazard ratio for treatment (PF-07321332 vs placebo), its CI, and p-value will be provided; and (2) Kaplan-Meier analysis where tabular summaries of the Kaplan-Meier curves providing the median, quartiles, and range will be provided for each treatment group. In addition, the KM curves will be presented graphically.

Imputation of missing data within efficacy variables and endpoints will be computed according to the rules specified in the SAP.

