### 9.3.4. Secondary Endpoint(s)/Estimand(s) Analyses

- Proportion of participants with severe signs/symptoms attributed to COVID-19 through Day 28
- Duration of each targeted COVID-19 sign/symptom
- Progression to a worsening status in 1 or more self-reported COVID-19 associated symptoms through Day 28
- Proportion of participants with a resting peripheral oxygen saturation ≥95% at Days 1 and 5.
- Proportion of participants with death (all cause) through Week 24

- PK of PF-07321332
- Viral titers (RT-PCR) measured in nasal swabs over time
- Number of COVID-19 related medical visits through Day 28.
- Number of days in hospital and ICU stay in participants with COVID-19 related hospitalization.

Details on the definitions and analyses of secondary endpoints will be described in the SAP.

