3.4. Baseline Variables

For viral load data, baseline visit is set up according to study days of Day -2 to Day 1. Only results that are within 1 hour post start of dosing will be treated as Baseline data. Laboratory assessments Signs and Symptoms, Vital Signs and ECG: Baseline window will be Day -2 to Day 1, without any consideration to the time factor.

The following baseline variables will be used in efficacy analyses. See below a list of derived baseline variables based on baseline viral load data:

- Baseline viral load defined as: $<10^4$ copies/mL vs $\ge 10^4$ copies/mL.
- Baseline viral load defines as: $<10^7$ copies/mL vs $\ge 10^7$ copies/mL.
- Baseline serology status defined as positive or negative.

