5. GENERAL METHODOLOGY AND CONVENTIONS

5.1. Hypotheses and Decision Rules

The primary hypothesis to be tested is whether or not there is a difference in proportion of participants with COVID-19 related hospitalization or death from any cause through Day 28 between PF-7321332/ ritonavir and placebo. The statistical hypothesis is as follows:

Ho:
$$\pi_{PF-7321332} - \pi_{placebo} = 0$$

versus
Ha: $\pi_{PF-7321332} - \pi_{placebo} \neq 0$ (1)

Where p PF-7321332 and p_{placebo} are the proportion of participants with hospitalization or death through Day 28. The hypotheses will be tested at an overall significant level of 5% (2-sided).

PFIZER CONFIDENTIAL
Page 18

Following the positive test of the primary endpoint, sequential testing will be performed for the following 2 secondary endpoints:

- Proportion of participants with COVID-19 related hospitalization or death from any cause through Day 28 who did not receive COVID-19 therapeutic mAb treatment, regardless of their onset of COVID-19 related signs and symptoms.
- Time (days) to sustained alleviation of all targeted signs/symptoms through Day 28.

The time to sustained alleviation of all targeted signs/symptoms through Day 28 will be tested first. If this test is positive, then will continue with second endpoint. The hypotheses will be tested at an overall level of 5% (2-sided).

Other secondary endpoints listed below will be subsequently tested following the Hochberg procedure¹:

- 1. Time (days) to sustained resolution of all targeted signs/symptoms through Day 28.
- 2. Proportion of participants with a resting peripheral oxygen saturation ≥95% at Days 1 and 5.
- 3. Number of COVID-19 related medical visits.

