5.2.3. Analyses for Categorical Endpoints

For categorical endpoints (ie, proportion of participants with a resting peripheral oxygen saturation \geq 95% at Days 1 and 5), proportion of participants for each category will be summarized for each group and a test for homogeneity of odds ratio using Breslow-Day test will be summarized.

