The count and proportion of participants with a resting peripheral oxygen saturation $\geq 95\%$ will be summarized by treatment group and by visits (Days 1 and 5). A cross table will be presented for both Day1 and Day 5, ie, for each proportion presented at Day 1, both proportions at Day 5 will be summarized. Treatment comparison between group for the odds ratio (baseline (Day 1) $\geq 95\%$ vs < 95) of comparing oxygen saturation $\geq 95\%$ at Day 5 will be analyzed with a Breslow-Day test for homogeneity of the odds ratios. The analyses will be done using mITT, mITT1, and mITT2 populations. Missing data at Day 1 or Day 5 will be excluded from the analysis.

6.2.9. Proportion of Participants with Death (all-cause) Through Week 24

The proportion of participants with death (all-cause) through Week 24 will be summarized by treatment group. Treatment comparison between the group will be presented as odds ratio and its 95% CI using logistic regression with a similar analysis model as specified in Section 6.1.1.2. The analyses will be done using mITT, mITT1, and mITT2 populations.

If zero counts are observed in either treatment group, the Fishers Exact test will be performed (instead of logistic regression) and pvalue provided.

As mortality is the most important of the efficacy at Week 24, this pertains specifically to that endpoint. If the impact s minimal (defined below), then no sensitivity analysis is required.

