6.6.3. Vital Signs

The measurement taken immediately prior to start of study drug will be used as the baseline for calculating changes in vital signs.

All vital sign data will be descriptively summarized by treatment group within SAS population and reported in accordance with the Pfizer Data Standards for safety reporting.

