Progression to a worsening status in 1 or more self-reported COVID-19- associated symptoms through Day 28.	Secondary analysis	mITT, mITT1 & mTT2	All data collected will be included regardless of intercurrent events. Use BOCF/LOCF for missing data. Use stratification variables as in Section 3.5.	Logistic regression
Proportion of participants with a resting peripheral oxygen saturation ≥95% at Days 1 and 5.	Secondary analysis	mITT, mITT1 & mTT2	All data collected will be included regardless of intercurrent events. Missing data will not be imputed.	Breslow-Day test for Homogeneity of the Odds Ratios
Proportion of participants with any signs/symptoms attributed to COVID-19 through Week 12 & Week 24.	Additional follow-up analysis	mITT, mITT1 & mITT2	All data collected will be included regardless of intercurrent events. Missing data will not be imputed.	Descriptive Statistics
Proportion of participants with death (all cause) through Week 24.	Secondary analysis	mITT, mITT1 & mTT2	All data collected will be included regardless of intercurrent events. Missing data will not be imputed. Use stratification variables as in Section 3.5.	Logistic regression or Fisher Exact test (if appropriate)
Viral titers measured via RTPCR in nasopharyngeal samples at Day 1 and Day 5.	Sensitivity analysis (POC)	mITT, mITT1 & mTT2	All data collected will be included regardless of intercurrent events. Use baseline viral load (continuous).	ANCOVA analysis

Endpoint	Analysis Type	Population	Data Inclusion and Rules for Handling Intercurrent Events and Missing Data	Analysis Model
Viral titers measured via RT-PCR in nasal swabs over time.	Secondary analysis	mITT, mITT1 & mTT2	All data collected will be included regardless of intercurrent events. Use baseline viral load (continuous).	MMRM analysis
Number of COVID-19 related medical visits.	Secondary analysis	mITT, mITT1 & mTT2	All data collected will be included regardless of intercurrent events. Missing data will not be imputed.	Descriptive statistics (based on negative Binomial Distribution)
Number of days in hospital and ICU stay in participants with COVID-19 related hospitalization.	Secondary analysis	mITT, mITT1 & mTT2	All data collected will be included regardless of intercurrent events. Missing data will not be imputed.	Descriptive statistics

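### SpO2 ≥95% is tested under Hochberg, but its only test (Breslow-Day) asks about treatment-by-baseline interaction, not about a treatment effect at Day 5

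*SAP*

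**What the plan says.** SAP 5.1 lists three secondary endpoints for the Hochberg procedure, after the primary endpoint and the two sequentially tested secondaries. The second of the three is "Proportion of participants with a resting peripheral oxygen saturation ≥95% at Days 1 and 5".

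Three places in the SAP give its analysis:

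- SAP 5.2.3 classes it as categorical and specifies proportions by category and "a test for homogeneity of odds ratio using Breslow-Day test".
- SAP 6.2.8 derives SpO2 as Yes (≥95%) or No (<95%), gives counts, proportions and a Day 1 by Day 5 cross table, and says the between-arm comparison of the Day 1 odds ratio "will be analyzed with a Breslow-Day test for homogeneity of the odds ratios". Participants missing a Day 1 or Day 5 value are excluded, and mITT, mITT1 and mITT2 are all to be used.
- SAP Appendix 1 gives the analysis model as "Breslow-Day test for Homogeneity of the Odds Ratios".

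Protocol 9.3.1 has a general rule for binary endpoints: "Treatment comparison between the group will be presented as the difference of proportions with its 95% confidence interval". The SAP's own binary list in 5.2.1 leaves SpO2 out, and Protocol 9.3.4 defers: "Details on the definitions and analyses of secondary endpoints will be described in the SAP". The neighbouring yes/no endpoints in SAP 6.2.5, 6.2.7 and 6.2.9 each get a logistic-regression treatment comparison.

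**The concern.** The endpoint is listed so that the drug can be compared with placebo. The p-value that enters Hochberg for it answers another question: whether Day 1 status predicts Day 5 status equally strongly in the two arms. A benefit or harm with the same odds ratio in both Day 1 groups satisfies that null hypothesis exactly, so the test would miss it about 95% of the time. A rejection has no direction and cannot be read as a higher Day 5 proportion.

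The same p-value also helps decide time to sustained resolution and number of medical visits, because Hochberg judges the three endpoints together.

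**Working it through.** **Sample size used.** The plan states no power for SpO2, so its primary sample size serves only as the N. The plan's 1717 comes from 7% vs 3.5%, 90% power and 5% two-sided (SAP 2.3). The pooled two-proportion formula gives, per arm, [1.960 × √(2 × 0.0525 × 0.9475) + 1.2816 × √(0.07 × 0.93 + 0.035 × 0.965)]² / 0.035² = (0.618 + 0.403)² / 0.001225 ≈ 852. That is 1704 in total, 0.8% below 1717. With 1:1 allocation, 1717 / 2 gives 858 per arm.

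**What the test compares.** In each arm, OR(arm) = odds of Day 5 ≥95% given Day 1 ≥95%, divided by the odds given Day 1 <95%. Rearranging,

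OR(active) / OR(placebo) = θ(high) / θ(low),

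where θ is the treatment odds ratio within a Day 1 group. Breslow-Day with arm as stratum therefore tests θ(high) = θ(low). On a worked 2×2×2 table, stratifying by arm or by Day 1 status gave p = 0.632 both ways.

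**Worked example (assumed rates).** Day 1 ≥95% in 85%; placebo Day 5 ≥95% in 90% of the high group and 45% of the low group.

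- Placebo odds are 9 and 0.818, so OR(placebo) = 11. Day 5 proportion: 0.85 × 0.90 + 0.15 × 0.45 = 83.25%.
- Treatment odds ratio 2 in both groups: odds 18 and 1.636, so OR(active) = 11, unchanged. Day 5 proportion: 0.85 × 0.947 + 0.15 × 0.621 = 89.8%, a gain of 6.6 points. Breslow-Day rejects in 5.2% of trials, the adjusted logistic test in 99.3%.
- Odds ratio 2 in the low group and 0.743 in the high group: the low group rises from 45% to 62.1% and the high group falls from 90% to 87.0%. The overall proportion stays at 83.25%. OR(active) = 6.685 / 1.636 = 4.09 against 11. Breslow-Day rejects in 91%, logistic in about 5%.

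**Simulation.** 20,000 trials per setting, 858 per arm, tests at 5% two-sided. There are nine scenarios: Day 1 ≥95% in 80-92%; placebo Day 5 ≥95% in 90-96% (high group) and 45-70% (low group). Logistic means the likelihood ratio test of treatment adjusted for Day 1 category.

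| True effect | Breslow-Day rejects | Logistic rejects |
|---|---|---|
| Constant OR 0.5 | 4.7-5.3% | 96-100% |
| Constant OR 1.5 | 4.7-5.3% | 43-80% |
| Constant OR 2 | 4.7-5.3% | 82-99.6% |
| Constant OR 3 | 4.7-5.3% | 99-100% |
| +3 points in both groups | 14-76% | 47-90% |
| -3 points in both groups | 9-24% | 40-69% |
| Proportion <95% halved in both groups | 6-25% | 88-100% |
| OR 2 in the Day 1 <95% group only | 30-68% | 16-52% |
| Equal Day 5 proportions (OR 2 low, 0.63-0.78 high) | 52-98% | about 5% |

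Breslow-Day also stays within 4.7-5.3% at OR 1. Mantel-Haenszel is within 0.004 of logistic at every range end. With 10% excluded for missing values (assumed; 772 per arm), constant OR 2 gives 4.7-5.2% against 78-99%, and equal proportions give Breslow-Day 48-96%.

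**Effect on the family.** With three endpoints, the Hochberg cut-offs are 0.05, 0.05 / 2 = 0.025 and 0.05 / 3 = 0.0167, from largest to smallest p-value. If the SpO2 p-value is the largest and exceeds 0.05, the next must be ≤0.025, or else the smallest ≤0.0167. Protocol 9.1 does not list the family and cites a false-discovery-rate paper for the procedure; under that method the second cut-off would be 2 × 0.05 / 3 = 0.033.

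**The case against.** **The protocol already covers it.** Protocol 9.3.1 promises a difference with 95% CI for binary endpoints. But the SAP classes SpO2 as categorical, omits it from its binary list, and governs secondary analyses. Even if the rule were read in, nothing would say which p-value enters Hochberg.

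**No error inflation when the drug does nothing.** This stands. With no effect in either Day 1 group, Breslow-Day holds its 5% size. The fault lies in power and interpretation.

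**The 52-98% figure is a constructed case.** This is fair: it needs harm in one Day 1 group to cancel benefit in the other. It shows what a rejection cannot mean, and is not a forecast.

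**Breslow-Day can be the more sensitive test.** With benefit only in the Day 1 <95% group it rejects more often than logistic (30-68% against 16-52%), and with 90-96% of the high group at ≥95% on placebo, that pattern is credible. A rejection would still show heterogeneity of odds ratios, not a higher Day 5 proportion.

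**The simulated model is simpler than the proposed one.** This is true. The SAP 6.1.1.2 model adds region, baseline viral load and serology, and its power was not simulated.

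**A correct null test would also raise the bar for the other two endpoints.** This is true. The fault is only that a different hypothesis decides it.

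**Conclusion.** Wrong as written, and it should be fixed. The p-value that SAP 5.1 takes into Hochberg does not test the endpoint listed there. The roughly 5% rejection rate under a constant odds ratio follows from the test's null hypothesis and does not depend on the SpO2 rates. The other percentages do depend on them, and those rates are assumptions because the documents give none.

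The impact is limited. The endpoint sits in the last testing tier, the primary and sequentially tested conclusions are unaffected, and proportions by arm and the cross table are still reported.

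**What to change.** In SAP 5.2.3, 6.2.8 and Appendix 1:

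- Replace Breslow-Day as the inferential test with one treatment comparison of Day 5 SpO2 ≥95%: the logistic regression of SAP 6.1.1.2 (likelihood ratio p-value) plus Day 1 category (≥95% vs <95%).
- Take that treatment p-value into Hochberg from one stated set, mITT as for the primary analysis; mITT1 and mITT2 are supportive.
- Report the difference in Day 5 proportions with 95% CI, as in Protocol 9.3.1.
- Keep Breslow-Day and the cross table as a descriptive interaction check.
- Define Day 1 category from the last pre-dose reading. SAP 3.4 and Appendix 2.1 say of vital signs "Baseline window will be Day -2 to Day 1, without any consideration to the time factor", whereas SAP 6.6.3 says "The measurement taken immediately prior to start of study drug will be used as the baseline for calculating changes in vital signs". Appendix 2.1 chooses among several readings by closeness to the target day, not by time of dosing. Protocol 1.3 already asks for baseline assessments before the first dose, so this makes the derivation match the intent.

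The cost is wording in three places and a standard model on data already collected. Amendment 4 says the interim objective had been met, and Protocol 6.3.2 provides for an unblinded submissions team. The change therefore needs a dated record that those making it had not seen treatment results. If that cannot be stated, the new comparison should be labelled post hoc.
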